5.2 Reporting Requirements

5.2.1 Reporting to the Institutional Review Board (IRB)

The IRB must be notified within 10 business days of "any unanticipated problems involving risk to subjects or others."

1. Any serious event (injuries, side effects, deaths or other problems), which in the opinion of the Principal Investigator was unanticipated, involved risk to subjects or others, and was possibly related to the research procedures.
2. Any serious accidental or unintentional change to the IRB-approved protocol that alters the level of risk.
3. Any deviation from the protocol taken without prior IRB review to eliminate apparent immediate hazard to a research subject.

-
4. Any new information (e.g., publication, safety monitoring report, updated sponsor safety report), interim result or other finding that indicates an unexpected change to the risk/benefit ratio for the research.
 5. Any breach in confidentiality that may involve risk to the subject or others.
 6. Any complaint of a subject that indicates an unanticipated risk or that cannot be resolved by the Principal Investigator.

5.2.2 Reporting to the FDA

The investigator or his designee must submit SAEs on FDA Form 3500A (MedWatch) according to the following reporting criteria:

- Reporting any unexpected fatal or life-threatening suspected adverse reactions no later than 7 calendar days after initial receipt of the information.
- Reporting any (1) serious, unexpected suspected adverse reactions, (2) findings from other clinical, animal, or in-vitro studies that suggest significant human risk, and (3) a clinically important increase in the rate of a serious suspected adverse reaction no later than 15 calendar days after determining that the information qualifies for reporting.

5.2.3 Reporting to Blue Earth Diagnostics

In addition to reporting of SAEs to the responsible IRB/IEC and Health Authority, Principal Investigator or designee will document all SAEs that occur following receipt of fluciclovine FI8 (whether or not related to study drug) to BED. Such SAEs must be reported within 24 hours of Principal Investigator or designee becoming aware of the event. All SAE information must be recorded and faxed or scanned and emailed to:

Blue Earth Diagnostics SAE E mail: [contact]
Tel: [name] ([name])
[contact]

Additional and further requested information (follow-up or corrections to the original case) will be detailed and faxed/emailed to the same address and must include the following minimum information: The name and contact information of the reporter, the name of the study drug(s), a description of the reported SAE, with the patient identified by one or more of the following (patient initials, patient number age, sex), an investigator assessment of study drug causality, and any additional data which would aid the review and causality assessment of the case including but not limited to the date of onset, severity, the time from administration of study drug(s) to start of the event, the duration and outcome of the event, any possible etiology for the event, and the final diagnosis or syndrome, if known.

6.0 Statistical Analysis

Primary Endpoint: To compare the number of biopsy-proven cancers that standard imaging would have missed compared with PET-hrMRI on mapping MRI (i.e. comparison of sensitivity of PET-hrMRI with mpMRI with biopsy-proven cancer as the gold standard).

Our preliminary data suggests that up to 60% of tumors invisible to standard mpMRI are detected on hrMRI. It is unclear how many additional lesions will be identified on fluciclovine PET-MRI. Since all areas of concern will be biopsied and only biopsy-proven tumors will be treated with HIFU, the morbidity of the surgical intervention is minimized and its potential to achieve cure is maximized.

Power Assessment: The power for the McNemar's type test proposed by Durkalski et al. (2003) is evaluated based on four correlations: r1: between lesions evaluated by PET-hrMRI for the same patient, r2: between lesions evaluated by mpMRI for the same patient, r3: between evaluations PET-hrMRI and mpMRI for the same lesion and r4: between evaluations PET-hrMRI and mpMRI for the different lesions at the same patient. In this way, we define four scenarios of correlation among lesions: (a) no correlation ($r1 = r2 = r4 = 0, r3 = 0.15$), (b) low correlation ($r1 = r2 = 0.1, r3 = 0.15, r4 = 0.015$), (c) medium correlation ($r1 = r2 = 0.4, r3 = 0.15, r4 = 0.06$) and (d) high correlation ($r1 = r2 = 0.8, r3 = 0.15, r4 = 0.12$). In addition, the number of lesions for each patient is defined as equal to 1 - 2 on average from preliminary data.

The minimum sample size to reach 80% of power is 22 patients when each patient has exactly 1 lesion (total of 22 lesions); 19 patients when the average number of lesions is 1.35 (total of 26 lesions); and 17 patients when the average number of lesions is 2 (total of 34 lesions). Given that our estimated number of biopsy-proven lesions per patient will be 1–2 based on historical data, we will proceed with a sample size of 20 patients.

Statistical Analysis: Sensitivities will be compared using McNemar's type test proposed by Durkalski et al. (2003) for cluster matched binary data. In addition, the 95% confidence interval for difference between sensitivities will be calculated as proposed by Yang et al. (2012).

Secondary Endpoints: Negative biopsy rate within treatment zones on standard 12-core biopsy 6 months following HIFU therapy; rate of high grade cancer in the untreated lobe.

Exploratory Endpoint: Formalin-fixed paraffin embedded biopsy tissue will be requested from a subset of patients for RNAseq transcriptome analysis. The number of cases analyzed will depend on availability of future funding. The subset of cases requested will depend on the exploratory object of the pilot study and may include discovery of signatures to predict presence of high grade cancer, unilateral disease or treatment success.

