Because the oncological effectiveness of HIFU depends on robust mapping and targeting of lesions within the prostate, improved detection of lesions using hrMRI and/or PET-MRI could provide a significant advantage in HIFU cancer control outcomes. Patients who are eligible for hemigland and focal HIFU absolutely depend on imaging for treatment planning; for example, in a patient with an index lesion of the right side of the prostate only, if imaging fails to detect a small focus of prostate cancer present on the left, hemigland HIFU (only treating the right side of the prostate) will not be effective at eradicating the entire bulk of his disease. It is even more important to accurately identify all prostate cancers when mapping for true focal therapy, since only identified lesions are ablated. We have previously shown that hrMRI detects up to 60% of tumors within the prostate not seen on mpMRI, and PET-MRI techniques may be able to improve the accuracy of this detection. Even if lesions that are ignored by mpMRI but detected on PET-hrMRI are indolent, long-term growth of these lesions may certainly affect cancer control outcomes over time and require costly and morbid retreatment. We believe that improved imaging at the outset of focal therapy would provide more comprehensive eradication of cancer burden from the start, resulting in improved long-term outcomes.

3.0 STUDY DESIGN:

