3.1 Overview

This prospective trial will evaluate the effectiveness of 18F-fluciclovine PET-hrMRI versus standard mpMRI at identifying prostate cancer targets for HIFU therapy. Patients with clinically localized, Gleason score 7-10 prostate cancer localized to one lobe on prior biopsies or overall Gleason score 6 with \geq half of systematic biopsy cores positive and \geq 50% of core involvement in at least one core, interested in HIFU would receive both a standard mpMRI and 18F-fluciclovine PET-hrMRI. They would then undergo a mapping biopsy using a standard sextant template plus MR/US-fusion targeted biopsy of any lesions with PI-RADS scores \geq 3 on hrMRI or 18F-fluciclovine PET positivity. The primary endpoint would assess the number of biopsy-proven cancers that mpMRI would have missed compared with hrMRI and/or 18F-fluciclovine PET. Following our tumor mapping study, patients with high grade disease (i.e. Gleason grade 4 or 5) in one lobe undergo hemigland or focal HIFU of that lobe. At 6 months, patients would undergo repeat mpMRI and prostate biopsy (MR/US-fusion biopsy plus standard sextant biopsy) to assess the negative biopsy rate in the treated region and absence of Gleason grade 4 or 5 in the untreated region as secondary endpoints

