3.3 Study endpoints

Primary Endpoint: To determine the number of biopsy-proven cancers that standard imaging would have missed compared with PET-hrMRI on mapping MRI

Secondary Endpoint: Negative biopsy rate on standard 12-core biopsy 6 months following HIFU therapy.

Exploratory Endpoint: RNAseq transcriptome analysis of lesions that are positive on mapping biopsy.

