If subjects are found to have unilateral high grade disease (i.e. Gleason grade 4 or 5), they will be considered as a candidate for hemigland or focal HIFU therapy. Clinician judgment may be exercised in determining eligibility for HIFU, since established criteria based on volume and extent of disease do not exist. If patients have high grade disease in both lobes, they will not be eligible for HIFU therapy on this trial. Their data will be used to assess the primary endpoint but they will not be considered for secondary endpoints.

HIFU Therapy and Follow Up Schedule

Patients who are eligible for HIFU will receive hemigland or focal HIFU per standard-of-care. All subjects will receive repeat mpMRI and MR/US-guided biopsy of all positive sites + systematic 12-core prostate biopsy at 6 months (or as clinically indicated). As an exploratory analysis, remnant formalin-fixed paraffin embedded tumor tissue will be requested for RNAseq transcriptome analysis of lesions that are positive on biopsy.

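### Read literally, the Section 6.0 secondary endpoints leave the unablated part of the treated lobe unscored after focal HIFU, whereas Sections 1.0, 3.1 and 3.3 would count a high-grade cancer there

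*Combined protocol and SAP*

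**What the plan says.** Four places state the 6-month outcome.

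- Section 6.0, in its paragraph on secondary endpoints, has: "Negative biopsy rate within treatment zones on standard 12-core biopsy 6 months following HIFU therapy; rate of high grade cancer in the untreated lobe".
- Section 3.1: the repeat biopsy is "to assess the negative biopsy rate in the treated region and absence of Gleason grade 4 or 5 in the untreated region as secondary endpoints". The abstract in Section 1.0 makes the same split between treated and untreated region.
- Section 3.3: "Negative biopsy rate on standard 12-core biopsy 6 months following HIFU therapy", with no limit to a zone and no high-grade component.

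On the extent of treatment, Section 3.1 says that men with high-grade disease "in one lobe undergo hemigland or focal HIFU of that lobe", and Section 3.4.2 (HIFU Therapy and Follow Up Schedule) says "Patients who are eligible for HIFU will receive hemigland or focal HIFU per standard-of-care". Section 2.8 explains why mapping matters most in true focal therapy: "since only identified lesions are ablated".

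Section 3.4.2 also provides for MRI, targeted cores and a systematic 12-core biopsy at 6 months. Men with high-grade disease in both lobes are left out of the secondary endpoints.

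**The concern.** Section 6.0 pairs a zone with a lobe. The two are complements only when the zone is a whole lobe, as in hemigland HIFU. In focal HIFU the ablated tissue is smaller than the lobe, and the remainder of that lobe is neither a treatment zone nor the untreated lobe.

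Take a man with focal HIFU to one lesion in the right lobe. At 6 months, a core from elsewhere in that lobe shows Gleason 4+3 and all other cores are clear. Under Section 6.0 he is negative in the treatment zone and has no high-grade cancer in the untreated lobe. Under Section 3.1 he is still negative in the treated region but counts against the second rate. Under Section 3.3 his biopsy is positive.

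This is the mapping failure that Section 2.8 warns about: a focus that imaging did not identify and that was therefore not ablated. An analyst who follows the statistical section to the letter would report the high-grade rate without it. Focal treatment is no side issue here, since it appears in the study title and in inclusion criterion 5.

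**Working it through.** The plan gives no target, power or number treated for the secondary endpoints, so there is no stated figure to reproduce. The check is a mapping of tissue to endpoint wording, followed by the arithmetic of one misclassified man.

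**Step 1. Where a high-grade cancer is scored, by location and wording.** Treatment zones and treated region are taken to mean ablated tissue.

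| Location at 6 months | Section 6.0 | Sections 1.0 and 3.1 | Section 3.3 |
|---|---|---|---|
| Ablated tissue | first component | first component | positive biopsy |
| Opposite lobe | second component | second component | positive biopsy |
| Unablated part of treated lobe (focal only) | neither | second component | positive biopsy |

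After hemigland HIFU the third row is empty and the wordings of 6.0 and 3.1 coincide. After focal HIFU they differ in that row only.

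**Step 2. Direction and size against Section 3.1.** Let N be the number of men treated and biopsied. Let C be the number with high-grade cancer in the opposite lobe. Let k be the number with high-grade cancer in the unablated part of the treated lobe but none in the opposite lobe.

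- Rate under 6.0 = C/N
- Rate under 3.1 = (C + k)/N
- Difference = k/N, which is never negative

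The high-grade rate under 6.0 therefore equals or understates the rate under 3.1, by 1/N for each affected man.

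**Step 3. Illustration.** N cannot exceed the planned 20. It will be smaller if any man is ineligible for HIFU after mapping. The values N = 15 and N = 10 are assumptions. With C = 0, and exact (Clopper-Pearson) 95% intervals:

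| N | k | Rate under 6.0 | Rate under 3.1 |
|---|---|---|---|
| 20 | 1 | 0% (0 to 16.8%) | 1/20 = 5% (0.1 to 24.9%) |
| 20 | 2 | 0% (0 to 16.8%) | 2/20 = 10% (1.2 to 31.7%) |
| 15 | 1 | 0% (0 to 21.8%) | 1/15 = 6.7% (0.2 to 31.9%) |
| 10 | 1 | 0% (0 to 30.8%) | 1/10 = 10% (0.3 to 44.5%) |

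The documents give neither the share of men who will have focal HIFU nor a rate for such cancers, so k cannot be predicted. It is zero if all men have hemigland HIFU, and also zero if no focally treated man has such a cancer.

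**The case against.** The strongest reply is that the gap exists in one of four statements. Sections 1.0, 3.1 and 3.3 all count the cancer, and the biopsy that finds it is taken regardless. This stands. A reader might infer that the protocol has no endpoint that registers such a cancer, or that the finding would be lost. The documents do not support either inference: the result will exist, and what is unsettled is which rate it enters.

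A second reply is that treatment zones is undefined and could mean the whole treated lobe, which would close the gap. That is possible, but no section says so. The same sentence of 6.0 uses lobe for the other component, and on that reading untreated tissue would be scored as treated. A definition is needed on either reading.

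A third reply concerns size. One could say that a third of the 12 cores go unscored after a one-sextant ablation, but the documents give neither the size of a focal zone nor the core layout, so that figure is not used here. Nor do the documents define a composite of success on both components; these are two separate rates.

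Finally, a reader might infer that any correction can only worsen the reported result. That holds for the high-grade rate of 6.0. It fails for 3.3, where limiting the unrestricted negative biopsy rate to treatment zones would make it more favourable.

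**Conclusion.** The point holds as an inconsistency in which the analysis section is the narrowest of four statements. If treatment zones means ablated tissue, Section 6.0 assigns the unablated part of a focally treated lobe to neither component. Sections 1.0 and 3.1, on the ordinary meaning of untreated region, assign it to the second, and 3.3 includes it without restriction.

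The effect on the high-grade rate is one-sided relative to 3.1. It is 5 percentage points per affected man at N = 20 and larger if fewer men are treated. Whether it is anything at all depends on the use of focal HIFU and on such a cancer occurring, and the documents give no figure for either. A claim that the reported outcome will be too favourable would go beyond them; the supportable claim is that the wording permits it. These are secondary rates with no stated power, and the primary comparison and the sample size do not change. The wording should be corrected before the outcomes are analysed.

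**What to change.** 1. In Section 6.0, replace the untreated lobe by the untreated region, defined as the opposite lobe plus any tissue of the treated lobe outside the ablation zone.
2. Define treatment zones as the ablated tissue, so that each 6-month core belongs to exactly one component.
3. Reconcile Sections 1.0, 3.1, 3.3 and 6.0. Section 3.3 needs the two components added, since it has no high-grade endpoint now. Keep its whole-gland 12-core negative biopsy rate as a reported rate alongside them, so that its result is not made more favourable.
4. Report each rate by ablation type (hemigland, focal), because the two types divide the gland differently.

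No extra biopsy or patient is needed. The cost is a rewording in these sections, a small table, and a data requirement: the ablation zone and the location of each 6-month core must be captured as study data. The documents do not say that either is recorded, but scoring within treatment zones, as Section 6.0 already intends, cannot be done without them. The change concerns scoring only and does not touch treatment.

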2.7 MR/US-Fusion for Targeting of Prostate Cancers

The advent of improved prostate imaging using multiparametric MRI and PET have dovetailed with advances in fusion software platforms that offer the ability to overlay static MRI images with real-time ultrasound images at the time of biopsy. This technology, called MR-US fusion, allows clinicians to target potential regions of interest in the prostate seen on mpMRI during an transrectal ultrasound-guided biopsy. Targeted MR-US fusion biopsies have been shown to significantly improve sensitivity and overall accuracy of biopsy over standard sextant biopsy by 24% and 14%, respectively. Most academic centers now offer MR-US fusion biopsies for patients with persistent rising PSA after negative standard biopsy and for surveillance biopsies while on active surveillance. MR-US fusion techniques are also being applied to focal ablation of prostate cancers with HIFU; both the Sonablate and Ablatheram HIFU platforms have announced partnerships with MR-US fusion companies to provide targeting during tumor ablation with HIFU. However, despite these improvements, the accuracy of targeted biopsy and targeted focal therapy is necessarily limited by accuracy of the MRI imaging for detection and localization of lesions.

2.8 Combining MR/US-Fusion, hrMRI, and PET-MRI with HIFU for Focal Treatment of Prostate Cancer

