PET scans involve injection of a radioisotope. Subjects undergoing a contrast-enhanced MR-PET will be screened using the standard clinical protocol to determine whether it is safe to administer contrast to the subject. An IV line will be inserted, and the participant will receive 10 mCi $\pm 20\%$ 18F-fluciclovine injection diluted up to 10mL injected via the IV, as an IV bolus injection followed by 10mL flush with normal saline solution. The participant will then be positioned supine in the scanner and will be scanned in the area of the prostate. The research PET scan will be a dynamic list mode scan. Meaning the PET would start first, then 18F fluciclovine would be injected immediately after the scan is started. For the PET acquisition, participants will be imaged for approximately 30 minutes.

All MRI images will be read according to PI-RADS (version 2) by a dedicated GU radiologists who has experience reading over 500 prostate MRIs. All PET scans will be

read by nuclear medicine co-investigators on the study ([name]). All lesions with PI-RADS greater than or equal to 3 and all PET positive areas will be considered suspicious for cancer. A region of interest (ROI) application will be used. The circumference of a suspicious lesion will be drawn on each individual MRI slice. The lesion volume and average ADC will be calculated from the ROI's. The tumor volumes and ADCs will be provided by the radiologist. To prevent the hrMRI from influencing the review of the mpMRI, all mpMRI's will be reviewed first. The radiologist will always be blinded to previous pathology.

Mapping Biopsy Protocols

After the pre-HIFU imaging protocol for tumor mapping, all patients will undergo a transrectal ultrasound-guided targeted mapping biopsy. The biopsy will include a standard sextant template plus MR/US-fusion targeted biopsy of any lesions with PI-RADS scores ≥ 3 on hrMRI or 18F-fluciclovine PET positivity. These areas will be targeted using the UroNav targeting software platform. As an exploratory analysis, remnant formalin-fixed paraffin embedded tumor tissue will be requested for RNAseq transcriptome analysis of lesions that are positive on mapping biopsy.

Eligibility for HIFU

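### The treated-zone result is scored on 12-core samples only, although targeted cores can qualify a man for HIFU, are taken again at 6 months, and count under Section 3.1

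*Combined protocol and SAP*

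**What the plan says.** **Before HIFU.** Under Mapping Biopsy Protocols (Section 3.4.2), "The biopsy will include a standard sextant template plus MR/US-fusion targeted biopsy" of suspicious lesions. On who may be treated, the same section says "If subjects are found to have unilateral high grade disease (i.e. Gleason grade 4 or 5), they will be considered as a candidate", with clinician judgment allowed. No core type or minimum number of positive cores is set.

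**At 6 months.** The follow-up schedule in Section 3.4.2 says "All subjects will receive repeat mpMRI and MR/US-guided biopsy of all positive sites + systematic 12-core prostate biopsy at 6 months". The Study Calendar likewise marks both a sextant and a targeted biopsy.

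**What is scored.** There are two answers:
- Section 3.3: "Negative biopsy rate on standard 12-core biopsy 6 months following HIFU therapy". Section 6.0 adds the restriction to the zone: "Negative biopsy rate within treatment zones on standard 12-core biopsy 6 months following HIFU therapy".
- Section 3.1: "prostate biopsy (MR/US-fusion biopsy plus standard sextant biopsy) to assess the negative biopsy rate in the treated region".

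No section says how a positive 6-month targeted core counts when the 12-core is clear. None pairs the 6-month result with the mapping result, or separates men whose treated zone was clear on template cores at mapping.

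**The concern.** Under Sections 3.3 and 6.0, disease can be established with one set of cores and its clearance judged with a narrower set. A man whose zone cancer was found only by a targeted core was already negative in that zone on the template. If HIFU leaves the cancer in place and the template misses it again, he is scored negative. A targeted core that finds the residual cancer does not change that score.

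The trial has a single arm, and this rate is its only listed measure of HIFU effect in the treated zone. Targeted-only lesions are to be expected: the trial adds imaging to find lesions otherwise missed, and Section 2.7 credits fusion targeting with the ability to "improve sensitivity and overall accuracy of biopsy over standard sextant biopsy by 24% and 14%, respectively". Leaving two definitions in the plan also lets the core set be chosen after results are known.

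**Working it through.** **The plan's own figure.** None exists for this endpoint: no target rate, threshold or sample size. The 80% power at n=20 belongs to the imaging comparison and does not bear on this point.

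**Inputs**
- S, the chance that the template detects cancer present in the zone: 0.5, 0.6 or 0.7. *Assumption; not in the documents.*
- t, the same chance for targeted cores: S + 0.24 or 1.24 × S. The 24% is from Section 2.7, which does not say whether it is absolute or relative. Targeted hits are assumed independent of template hits, with mapped sites targeted again at 6 months.
- HIFU has no effect, so cancer is always still present. Grade is ignored.

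**Formulas**
- Share of treated men positive on targeted cores only at mapping: f = (1−S)t / [S + (1−S)t].
- q and m: chance of a negative 6-month template in men who were template-negative and template-positive at mapping.
- No-effect negative rate on the 12-core: r = f·q + (1−f)·m. Excess from mixing in targeted-only men: r − m = f(q − m).
- Equal detectability: q = m = 1−S, so the excess is 0.
- Varying detectability, Beta with a+b=2 and mean S: m = 2(1−S)/3 and q = 1 − 2S/3, so q − m = 1/3 and the excess is f/3.
- No-effect negative rate on template plus targeted cores: r(1−t).

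| S | t | f | r, equal | r, varying | excess, varying | all cores, equal | all cores, varying |
|---|---|---|---|---|---|---|---|
| 0.5 | 0.74 | 43% | 50% | 48% | 14 points | 13% | 12% |
| 0.5 | 0.62 | 38% | 50% | 46% | 13 points | 19% | 18% |
| 0.6 | 0.84 | 36% | 40% | 39% | 12 points | 6% | 6% |
| 0.6 | 0.744 | 33% | 40% | 38% | 11 points | 10% | 10% |
| 0.7 | 0.94 | 29% | 30% | 30% | 10 points | 2% | 2% |
| 0.7 | 0.868 | 27% | 30% | 29% | 9 points | 4% | 4% |

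Example, first row: f = 0.5 × 0.74 / (0.5 + 0.37) = 0.425; excess = 0.425/3 = 0.142, or 2.8 men if all 20 were treated.

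**Allowing for the entry biopsy.** Inclusion requires a qualifying biopsy of at least 10 cores. Suppose it sampled the same zone on a similar template, which is not stated. Detectability then follows Beta(2S+1, 2(1−S)), with mean (2S+1)/3 and q − m = 1/4. This gives f = 18-27%, r = 19-32% and an excess f/4 of 4-7 points. The equal-detectability case is unchanged.

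**With a real HIFU effect.** If a fraction c is truly cleared, independently of detectability, the reported rate is c + (1−c)r. Take an illustrative c = 0.60, S = 0.6 and equal detectability. The 12-core alone gives 0.60 + 0.40 × 0.40 = 76%. All cores give 0.60 + 0.40 × 0.064 = 63% to 0.60 + 0.40 × 0.102 = 64%. At c = 0.80 the figures are 88% against 81-82%.

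**A looser bracket.** Without the Beta model, taking f = 0.10-0.40, q = 0.5-1.0 and m = 0 gives f·q = 5-40 points. The top end needs the template to hit some lesions every time and miss the others every time, so I do not rely on it.

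**The case against.** The strongest reply is that Section 3.1 already counts fusion cores and Section 3.4.2 already collects them. On template plus targeted cores, essentially every treated man is positive at mapping, because that result made him a candidate. A conversion rate would then equal the overall rate. This stands. A reader might infer that the baseline is missing whichever cores are used; it is not, and the problem belongs to the 12-core reading. One limit remains: the sites to be targeted at 6 months are not defined, and repeat imaging is mpMRI only, so a site first seen on PET-hrMRI may not be sampled again.

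Other points that stand:
- A reader might infer that one positive core of any kind leads to HIFU. The plan requires high-grade disease confined to one lobe, plus clinician judgment. A single targeted core is merely not ruled out.
- A targeted-only man is not automatically a success; the template must miss again. If his high-grade disease was targeted-only but template cores in the zone held lower-grade cancer, he was not template-negative under a plain reading of a negative biopsy.
- It is tempting to treat the whole 29-50% as the error. Most of it is ordinary repeat-sampling miss: template-positive men alone would still show 20-33% (varying detectability) or 30-50% (equal). Restricting the denominator removes only the excess.
- The endpoint is secondary and descriptive, and HIFU is standard of care. The 89% negative histology in Section 2.3 is background; no comparison with it is planned.

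The entry biopsy lowers the share of targeted-only zones but does not abolish it. It predates mapping, and the Gleason 7 or higher route names no core type.

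**Conclusion.** The point holds as a conflict over which cores define the treated-zone result, and it has a direct consequence. Under Sections 3.3 and 6.0, a man positive only on targeted cores at mapping can be scored negative with no ablation effect, and contrary 6-month targeted evidence is left out. Section 3.1 says otherwise.

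The size cannot be derived from the documents. Under an assumed template sensitivity of 50-70%, the excess from mixing in targeted-only men is 0 points with equal detectability, about 9-14 points under the Beta model, and about 4-7 points if the entry biopsy is modelled as well. The choice of cores matters more: counting targeted cores takes the no-effect negative rate from 29-50% to about 2-19%, provided the mapped sites are sampled again.

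The documents do not support saying that HIFU success is inflated by a known amount, or that the primary imaging endpoint is affected. The point is worth settling before results are seen.

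**What to change.** First confirm whether the mapping sextant template and the 6-month 12-core sample the same sites. The Study Calendar lists them in one row, which suggests so, but the text does not say it. Then, in Section 6.0, with Sections 3.1 and 3.3 aligned:

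1. Define the treated-zone negative rate on all 6-month cores from that zone, template plus targeted, over all treated men.
2. Report the 12-core-only rate as a secondary line, in a table paired with the mapping template result for the same zone. Put men positive only on targeted cores at mapping in their own row and do not count them there as conversions.
3. Keep the overall 12-core rate over all treated men as a descriptive line.
4. State what the 6-month targeted sites refer to, and report for how many treated zones the mapped target was sampled again.

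The cost is SAP wording and one small table from cores already planned; there is no extra biopsy or visit. The downside is a probably less favourable rate and small rows. The template-positive row would lose about 27-43% of at most 20 treated men under the assumptions above, or 18-27% if the entry biopsy is modelled with varying detectability. Pairing shows repeat-sampling misses but does not remove them.
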